9. PRE-STUDY AND CONCOMITANT INTERVENTION/MEDICATION

Concomitant medications will be documented during screening and updated during the study. Disallowed concomitant interventions for this study include ocular medications of any kind, or any systemic medications that would normally contraindicate contact lens wear or may otherwise compromise study endpoints.

9.1. Systemic Medications

Certain systemic medications are known to have a higher likelihood to interfere with contact lens wear, chiefly by disrupting the tear film.

A summary of disallowed systemic medications is shown in Table 4. Subjects with a history of taking these medications will be allowed to enroll only if:

- The medications have been taken on a continual, routine basis for at least 6 months, and
- The subject has demonstrated successful contact lens wear during this time.

Or:

- The subject was taking the medication on a temporary basis and ceased taking that medication at least 2 weeks prior to signing the informed consent (this is considered sufficient time for the medication to have left the body prior to enrollment).

Subjects with a history of taking medications listed in Table 4 on a long-term, routine basis for less than 6 months will not be allowed to participate in the study.

Table 4: Disallowed systemic medications

Class of Drug	Common Indication(s)	Common Examples
Estrogens (not including contraceptive medication)	Menopause, osteoporosis, vaginitis	Vagifem, Estrace, Climara, Vivelle-Dot, Premarin, Minivelle, etc.
Anticholinergics	Irritable bowel syndrome, Parkinson's disease, peptic ulcer, cystitis, nasal congestion, cold symptoms, overactive bladder, COPD	Bentyl, Spiriva, Atrovent, Hyosyne, Levsin, Symax Fastab, Symax SL, Homax SL, Cogentin, Transderm Scop, etc.
Beta-blockers	Hypertension, angina, heart attack, migraine, atrial fibrillation, adrenal cancer, essential tumor, glaucoma	Toprol XL, Lopressor, Tenormin, Propranolol, Timoptic, Trandate, Inderal LA, etc.
Psychotropics	Antipsychotic (schizophrenia, mania), antidepression, antiobsessive, antianxiety, mood stabilizer, stimulants (ADHD)	Zoloft, Celexa, Prozac, Lexapro, Effexor, Cymbalta, Ativan, Xanax, Desyrel, Wellbutrin, etc.

Clinical Study Protocol

Johnson & Johnson Vision Care, Inc.

Class of Drug	Common Indication(s)	Common Examples
Vitamin A analogs	Cystic acne	Isotretinoin

Examples of disallowed systemic antihistamines are given in Table 5. Subjects with a history of taking systemic antihistamines will be allowed to enroll only if:

- They have taken antihistamines continuously for at least 2 weeks, and
- They have demonstrated successful wear while taking the medication

Or:

- They stopped taking the medication for at least 2 weeks prior to enrollment.

Table 5: Disallowed systemic antihistamines

Class of Drug	Common Indication(s)	Common Examples
Antihistamines	Allergic rhinitis, sedation, hives, allergic conjunctivitis, skin allergy, itching, motion sickness	Hydroxyzine, Promethagan, Phenadoz, Vistaril, Claritin, Zyrtec, Astepro, Astelin, Optivar, Allegra, Benadryl, etc.

10. DEVIATIONS FROM THE PROTOCOL

Investigator will notify study sponsor upon identification of a protocol deviation. Protocol deviations must be reported to the sponsor within 24 hours after discovery of the protocol deviation. The Investigator will report deviations per IRB/IEC requirements. All deviations will be tracked, and corrective actions implemented as appropriate.

If it becomes necessary for the Investigator to implement a deviation in order to eliminate an immediate hazard to the trial subject, the Investigator may implement the deviation immediately without notification to the sponsor. Within 24 hours after the implemented deviation, the Investigator must notify and provide the rationale to the Sponsor and, as required, the IEC/IRB.

If the deviation potentially impacts the safety of patient or changes the technical integrity of the study, then it must be reported to IEC/IRB. This is a "Major Deviation". Deviations that contradict the information contained in the Informed Consent/Accent forms will be considered Major Deviations.

Minor deviations have no substantive effect on patient safety or technical integrity of the study. They are often logistical in nature.

Protocol waivers are prohibited.

Clinical Study Protocol
Johnson & Johnson Vision Care, Inc.

Table 6 lists examples of deviations that will constitute major and minor protocol deviations for this study.

Table 6: Examples of major and minor protocol deviations

Deviation category	Major deviation	Minor deviation
Out-of-window visit	Visit attended > 3 days out of visit window defined in study procedures	Visit attended \leq 3 days out of visit window defined in study procedures
Unanswered PRO questions	For questionnaires where data is related to a primary or secondary endpoint, > 2 PRO questions are unanswered (i.e., left blank).	For questionnaires where data is related to a primary or secondary endpoint, \leq 2 PRO questions are unanswered (i.e., left blank). For questionnaires where data where data is not related to a primary or secondary endpoint, any PRO questions are unanswered (i.e., left blank).
Non-compliance with wear schedule	Subject does not wear study lenses for at least 8 hours on at least 5 days of a study lens wear period. Subject wears their habitual contact lenses during any of the study lens wear periods. Subject wears contact lenses during the wash-in or washout periods.	Subject does not wear study lenses for at least 1 hour prior to attending a follow-up visit.

In the case of a major protocol deviation, the decision of whether or not the subject will be excluded from the Per-Protocol analysis population will be made at the time of cohort review.

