5.3. Procedures for Maintaining and Breaking the Masking

Two randomization codes (alphanumeric characters) will be generated, one for the AO1D lens and one for the AO1DfA lens, using the form [REDACTED]. Study lenses will be supplied in blister packs labelled with the study number, lot number, sphere power, expiration date and the randomization codes. Sponsor personnel involved in the conduct of the trial will not be masked to the identity of study lenses.

When dispensing test articles, the following steps should be followed to maintain randomization codes:

1. Investigator or designee (documented on the Delegation Log) will consult the lens fitting schedule to obtain the test article assignment for that subject prior to dispensing.
2. Investigator or designee will record the subject's number on the appropriate line of the lens fitting schedule.
3. Investigator or designee will pull the appropriate test articles from the study supply. All test articles that are opened, whether dispensed (placed/fit on eye or dispensed outside the clinical site) or not, must be recorded on the Test Article Accountability Log in the "Dispensed" section.

Under normal circumstances, the mask should not be broken until all subjects have completed the study and the database is finalized. Otherwise, the mask should be broken only if specific emergency treatment/course of action would be dictated by the subject knowing their treatment status. In the event the mask is broken, the sponsor must be informed as soon as possible. The date, time, and reason for the unmasking must be documented in the subject record.

Subjects who have had their treatment assignment unmasked are expected to return for all remaining scheduled evaluations. If necessary, subjects who are discontinued may be replaced to reach the subject completion target.

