14.3. Analysis Populations

Safety Population:

All subjects who are administered any test article excluding subjects who drop out prior to administering any test article. At least one observation should be recorded.

Per-Protocol Population:

All subjects who successfully complete all visits and do not substantially deviate from the protocol as determined by the trial cohort review committee prior to database hard lock. Justification for the exclusion of subjects with protocol deviations from the per-protocol population set will be documented in a memo to file.

Intent-to-Treat (ITT) Population:

All randomized subjects regardless of actual treatment and subsequent withdrawal from the study or deviation from the protocol. At least one observation should be recorded.

[figure not shown]

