14.6. Secondary Analyses

The secondary analyses will be conducted on Intent-to-Treat populations to establish superiority and Per-protocol populations for non-inferiority.

CLUE Vision score – (S1)

CLUE vision scores at 1-week follow-up will be analyzed using a linear mixed effect model. This model will include the experimental design factors: sequence of lens wear, lens wearing period, lens type and the interaction between lens type and lens wearing period as fixed effects. Baseline characteristics known of importance such as age and gender will be included as fixed covariates. Site will be included as random effects (G-side). The covariance of residuals between of the same subject (R-side) across period will be modeled using either homogenous compound symmetry (CS) or unstructured (UN) covariance structure. The structure that returns the lowest finite sample corrected Akaike's Information criterion¹⁰ will be selected as the structure that best fits the model. The Kenward and Roger method will be used for the calculation of the denominator degree of freedom¹¹.

The null and alternative hypotheses for superiority of CLUE Vision for the Test (AO1DfA) minus Control (AO1D) is as follows:

$$H_0: \Delta \leq 0.0$$
$$H_A: \Delta > 0.0$$

where Δ is the least-square means (LSM) difference between the Test and Control lens (Test minus Control). Superiority for the Test to the Control lens will be established on ITT population if the lower bound of the 95% two-sided confidence interval (CI) for least squares mean (LSM) difference (Test - Control) of CLUE Vision score is greater than 0.

Visual Performance (HLHC logMAR) – (S2)

The comparison of Monocular distance visual performance of HLHC in logMAR scale between the Test (AO1DfA) to the Control (Spectacles) will be analyzed using a similar linear mixed effect model described in the primary analysis above. Since this endpoint for the Test lens (AO1DfA) will be collected before or after the Control (Spectacles) and no carryover effect is expected in objective visual performance, the lens wearing period can be defined accordingly.

The null and alternative hypotheses for non-inferiority of Test lens (AO1DfA) relative to Control (Spectacles) are as follows:

$$H_0: \Delta > 0.05$$
$$H_A: \Delta \leq 0.05$$

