where Δ is the mean difference in logMAR between Test lens and Control lens (Test minus Control). Non-inferiority will be declared on Per-protocol population if the upper bound of the (1- α) two-sided confidence interval of the mean difference between Test and Control is less than 0.05. The α is the Type I error derived from Gatekeeping strategy and α -propagation in Section 14.4. If the non-inferiority is established, superiority will be declared

Clinical Study Protocol

Johnson & Johnson Vision Care, Inc.

if the upper bound of the confidence interval of the mean difference between Test and Control is less than 0.0.

Contact Lens Preference – (S3)

Contact lens preference question will be analyzed using a baseline-category logistic model, where the response of the Control lens preference is the baseline category. This model will include the experimental design factors: sequence of lens wear, lens wearing period, lens type and the interaction between lens type and lens wearing period as fixed effects. Baseline characteristics known of importance such as age and gender will be included as fixed covariates.

The null and alternative hypotheses for superiority of Test (AO1DfA) lens relative to Control (AO1D) are as follows:

$$H_0: \Delta \leq 1.0$$
$$H_A: \Delta > 1.0$$

where Δ is the odds of the preference for the Test to the preference for the Control (Test divided by Control). Superiority for the Test to the Control lens will be established on ITT population if the lower bound of the $(1 - \alpha)$ % two-sided confidence interval (CI) for least squares mean (LSM) odds (Test divided by Control) of the contact lens preference is greater than 1.0. The α is the Type I error derived from Gatekeeping strategy and α -propagation in Section 14.4.

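### Non-inferiority to spectacles (S2) rests on the per-protocol set alone, with discretionary exclusions and an all-visits rule that drops complete toric-spectacle pairs; a shift of about 0.005 logMAR could change the result

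*Combined protocol and SAP*

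**What the plan says.** Section 14.6 divides the secondary analyses by type of claim: ITT for superiority and "Per-protocol populations for non-inferiority". For S2 it repeats the rule: "Non-inferiority will be declared on Per-protocol population", if the upper confidence limit for AO1DfA minus spectacles is below 0.05 logMAR. No ITT condition or sensitivity analysis is attached to that claim, and Section 14.9 rules out imputation.

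Section 14.3 defines the per-protocol set as "All subjects who successfully complete all visits and do not substantially deviate from the protocol as determined by the trial cohort review committee". The decision comes before hard lock, and the justification for exclusions "will be documented in a memo to file". Section 10 states that Table 6 "lists examples of deviations that will constitute major and minor protocol deviations for this study". Those examples do not exclude a subject automatically. For a major deviation, the decision on per-protocol membership "will be made at the time of cohort review".

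On masking, Section 5.2 leaves investigators and site staff unmasked, and Section 5.3 adds that "Sponsor personnel involved in the conduct of the trial will not be masked to the identity of study lenses". The membership of the cohort review committee, its masking and the data it sees are not described.

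In Section 7.2, spectacle acuity is measured at Visit 4 (step 4.6), before the second lens is fitted.

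**The concern.** A per-protocol analysis is a normal choice for non-inferiority. The difficulty is that it stands alone here and that membership is partly a matter of judgement after randomisation. If the excluded subjects have a different toric-minus-spectacle difference from those kept, the estimate moves against a fixed margin, and the plan requires no second analysis to agree before the claim is made.

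The all-visits rule adds a separate loss. In the toric-first sequence the S2 pair is complete at step 4.6. A subject who then fails the spherical fit, over-refraction or dispensing check is discontinued and leaves the S2 analysis, although both S2 measurements exist.

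At stake is the secondary claim against spectacles. Because S2 and S3 share alpha by the Holm procedure (Section 14.4), an S2 result that turns on exclusions can also change the alpha available to S3.

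**Working it through.** **Inputs.** From Table 10: SD 0.09, N = 153, intraclass correlation (ICC) 0.3, 0.4 or 0.5, and the less favourable true difference of 0.030. From Section 14.6: margin 0.05. From Section 14.2: paired t test. From Section 14.4: S2 is tested at two-sided 0.025 or 0.05, depending on S3. The documents give no rate of per-protocol exclusion.

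**The plan's own figure.** With paired SD = SD × √(2(1 − ICC)) and effect 0.05 − 0.030 = 0.020, one-sided 0.025 gives power 0.636, 0.703 and 0.780 at ICC 0.3, 0.4 and 0.5. Table 10 prints 0.703, 0.780 and 0.863 for type I error 0.025. The printed values match ICC 0.4, 0.5 and 0.6, so the columns appear shifted by one. That is a separate matter; the check below uses only the SD, N and ICC.

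**Room below the margin (ICC 0.4, 95% two-sided interval).**
- Paired SD = 0.09 × √(2 × 0.6) = 0.0986.
- Half-width = 1.976 × 0.0986 / √153 = 0.0157.
- Non-inferiority therefore needs an observed mean below 0.05 − 0.0157 = 0.0343.
- An observed 0.030 has an upper limit of 0.0457, which leaves about 0.004.
- At two-sided 0.025 the half-width is 0.0180, the upper limit 0.0480 and the room 0.002.

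**Effect of exclusions.** The full-set mean exceeds the per-protocol mean by the excluded fraction times the excess difference among those excluded. Assume 10% are excluded and are 0.05 worse: 0.10 × 0.05 = 0.005. A per-protocol mean of 0.030 on 138 subjects then corresponds to 0.035 on all 153. Upper limits of the 95% interval:

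| ICC | Per-protocol (0.030, n = 138) | All subjects (0.035, n = 153) |
|---|---|---|
| 0.3 | 0.0479 | 0.0520 |
| 0.4 | 0.0466 | 0.0507 |
| 0.5 | 0.0451 | 0.0494 |

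The per-protocol analysis passes in all three rows. The full set fails at ICC 0.3 and 0.4 and passes narrowly at 0.5.

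**How few subjects matter.** At ICC 0.4, take a narrow failure with mean 0.0363 and upper limit 0.052. Removing two subjects 2 SD above the mean, three at 1.5 SD or four at 1 SD brings the limit below 0.05.

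**Error rate at the margin.** In simulation (40,000 trials, true difference 0.05, ICC 0.4), removing 5%, 10% or 15% of subjects without regard to outcome leaves one-sided error at about 0.025. If those same fractions are reviewable and only subjects with a worse-than-average difference are removed, it rises to about 0.044, 0.071 and 0.117. This is a worst case under assumed rates, not a prediction.

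**The case against.** The strongest reply is that the plan follows convention and has safeguards. Review precedes hard lock, exclusions are justified in writing, waivers are prohibited (Section 10) and changes to the analysis must be reported (Section 14.10). S2 is tested only after the primary hypothesis and S1 succeed, and study success depends on the primary hypothesis alone (Section 2.3), analysed on ITT. All of this stands and limits the weight of the point. A memo records an exclusion but does not show whether the conclusion would hold without it.

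The second reply concerns masking. A reader might infer that because staff know the lens, the committee can steer the result. The documents do not support that. S2 is a within-subject contrast, so an exclusion removes the toric and spectacle readings together, and lens identity alone says little about the direction of the effect. Sight of acuity would be needed. The documents do not say that the committee has it; they only fail to say that it does not.

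Third, a reader might take the failed spherical fit as evidence of bias. It is not: all-visits is a fixed criterion, and loss for a reason unrelated to the S2 contrast mainly costs precision.

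Fourth, S2 includes a superiority step after non-inferiority, and superiority is assigned to ITT. The plan therefore arguably already calls for an ITT interval on this contrast. That is a fair reading, but the text is unclear and does not make ITT a condition for non-inferiority.

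**Conclusion.** The point holds as a weakness in a gated secondary claim. Non-inferiority depends on one analysis set, membership after a major deviation is discretionary, masking of the review to acuity is not stated, and complete toric-first pairs can be discarded. At SD 0.09, n = 153 and ICC 0.4, an observed 0.030 leaves about 0.004 logMAR below the margin, so a shift of about 0.005 can change the conclusion. This rests on the plan's planning values and on an assumed 10% excluded with a 0.05 worse difference. At ICC 0.5 and the 95% interval, the same shift does not change the result.

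A larger effect is tempting: 20% excluded and 0.10 worse gives 0.20 × 0.10 = 0.020, the whole distance from 0.030 to 0.05. That would need a fifth of subjects to average about one paired SD (0.099) worse, and nothing in the documents points to so large a shift. The documents also give no ground for saying that exclusions will be selective.

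**What to change.** - **Section 14.6:** run the same S2 model on ITT, and declare non-inferiority only if the upper limit is below 0.05 in both the per-protocol and ITT sets.
- **Section 14.3:** for S2, require only the visits that supply the toric and spectacle acuity.
- **Section 10:** have the cohort review decide exclusions without sight of acuity data, from an S2-specific list of deviations that bear on toric or spectacle acuity. Not all Table 6 major deviations belong there: blank questionnaire items or under-wear in the spherical period would remove valid S2 pairs.
- **Sections 8.2 and 10:** reconcile them. The first says that subjects not compliant with the protocol or wear schedule will be withdrawn; the second treats such non-compliance as a deviation for cohort review.

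The cost is wording, one more model run and slightly lower power, since two limits must clear the margin. Joint power cannot exceed that of the per-protocol test. At a true difference of 0.030, ICC 0.4 and one-sided 0.025, that test has power 0.703 with 153 subjects, 0.680 with 145 and 0.658 with 138. Keeping complete toric-first pairs recovers some of this.

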11. STUDY TERMINATION

The occurrence of one or more Unanticipated Serious Adverse Device Effect (USADE), or any SAE where the relationship to study agent cannot be ruled out, may result in stopping further dispensing of test article. In the event of a USADE or SAE, the Sponsor may unmask

Clinical Study Protocol

Johnson & Johnson Vision Care, Inc.

the treatment regimen for the subject(s) and will discuss this with the Investigator before any further subjects are enrolled.

The Sponsor will determine when a study will be stopped. The Principal Investigator always has the discretion to initiate stopping the study based on patient safety or if information indicates the study's results are compromised.

JJVC reserves the right to terminate the study at any time for any reason. Additionally, the IEC/IRB reserves the right to terminate the study if an unreasonable risk is determined. The study can be terminated by the Principal Investigator at the individual clinical site due to specific clinical observations, if in their opinion, after a discussion with JJVC, it is determined that it would be unwise to continue at the clinical site.

JJVC (and the IEC/IRB and DMC, if applicable) will evaluate all adverse events. If it is determined that an adverse event presents an unreasonable risk, the investigation, or that part of the investigation presenting the risk, will be terminated as soon as possible.

Should the study be terminated (either prematurely or as scheduled), the Investigator will notify the IEC/IRB and Regulatory Authority as required by local regulatory requirements.

12. PROCEDURE FOR HANDLING PRODUCT QUALITY COMPLAINTS

A Product Quality Complaint (PQC) refers to any written, electronic, or oral communication that alleges deficiencies related to the identity, quality, durability, reliability, safety, effectiveness or performance of test articles after they have been released for clinical trial use.

Potential complaints may come from a variety of sources including but not limited to subjects, clinical research associates (CRA), clinical operations managers (COM), medical monitors, and site personnel, etc. The following are not considered product quality complaints:

- Subject satisfaction inquiries reported via "Subjective Questionnaires" and "Patient Reported Outcomes (PRO)."
- Clinical test articles that are stored improperly or damaged after receipt at the investigational site.
- Lens replacements that occur due to drops/fall-outs.
- Damage deemed by clinicians or clinical staff to be caused by handling by the user, and not indicative of a quality deficiency (i.e. tears, rips, etc.), only in situations where there is no deficiency alleged by the subject.

Within 24 hours of site personnel becoming aware that a PQC has occurred, the PQC must be recorded in the EDC system, which will trigger an automatic email notification to the appropriate COM/CRA and Clinical QA representative. In cases where the EDC system in use is not configured to send automatic notifications or when an EDC system is not used, the COM/CRA is responsible for notifying Clinical QA upon discovery that a PQC has occurred.

Clinical Study Protocol

Johnson & Johnson Vision Care, Inc.

Upon receipt of the EDC notification, the COM/CRA will contact the study site to collect additional information which will include:

- Date the complaint was received/recorded in the EDC System (Date of Sponsor Awareness).
- Who received the complaint.
- Study number.
- Clinical site information (contact name, site ID, telephone number).
- Lot number(s).
- Unique Subject Identifier(s).
- Indication of who first observed complaint (site personnel or subject).
- OD/OS indication, along with whether the lens was inserted.
- Any related AE number if applicable.
- Detailed complaint description (scheduled/unscheduled visit, wear time, symptoms, resolution of symptoms, etc.).
- Eye Care Provider objective (slit lamp) findings if applicable.
- Confirmation of product availability for return (and tracking information, if available), or rationale if product is not available for return [REDACTED]

Once a complaint is received, it will be assessed by the COM, CRA, or trained site personnel to determine if it is an Adverse Event/Serious Adverse Event (AE/SAE). If the complaint results in an AE/SAE, the COM/CRA, or trained site personnel will follow section 13 of this protocol. If the AE/SAE was potentially the result of a product quality related deficiency, these procedures also applies and will be executed in parallel.

In some cases, a PQC form may be generated in EDC by the site in error. In this event, the PQC forms will be marked “Intentionally Left Blank” or “ILB”. Justification for ILB must be documented.

